Abbreviated Title:	Participant Satisfaction with the BUILD Mobile Application
Sponsor:	Woebot Health
Study Type:	Product learning
Number of Participants:	~165 (150 complete)
Number of Sites:	1
Study Objective:	The overarching goal of this study is to explore satisfaction with a version of Woebot that leverages Large Language Models (LLMs) to recreate core therapeutic experiences. As a benchmark for understanding the relative performance, this LLM MVP of Woebot will be compared against a version of Woebot that does not use LLMs.
Primary Aim and Endpoint:	Aim: To explore user satisfaction with the DISC-MVP Endpoints: Client Satisfaction Questionnaire for both treatment groups.
Secondary Aims and Endpoints:	Aim: To explore user satisfaction with DISC-MVP for users with mild symptomatology or above (PHQ-8 or GAD-7 \geq 5). Endpoint: Client Satisfaction Questionnaire for both treatment groups.
	[REDACTED]

	
Study Design:	Randomized controlled trial
Study Duration:	2 week intervention period
Target Population:	Adults with or without clinical symptoms
Key Inclusion Criteria:	
1. Be 18+ years of age and older (no upper limit)2. Own or have regular access to a smartphone with a recent operating system installed (Android: OS 8.0 or higher, Apple: iOS 13.0 or higher) with reliable Wi-Fi access or sufficient data plan to engage with assigned treatment condition for the duration of the study3. Available and committed to engage with the program and complete assessments for a 2-week duration4. Able to read and write in English5. Participants must have primary residence in the United States
Key Exclusion Criteria:	
1. Current suicidal ideation with a plan and/or intent or a suicide attempt within the past 12 months2. Previous Woebot use
Study Conditions:	DISC-MVP

	DISC-CON
Test Device:	DISC-MVP
Control Device:	DISC-CON
Statistical Methods:	Descriptive statistics will be reported for study measures for each study arm as well as the total sample. Summary reports will be presented for all time periods independently. [REDACTED] [REDACTED] [REDACTED] [REDACTED] [REDACTED]
Protocol Version and Date:	1.1 (8/SEP/2023)
Keywords:	digital mental health intervention, chatbot, conversational agent, relational agent, natural language processing, artificial intelligence

Table of Contents

Schedule of Events	12
1. Introduction	13
1.1 Background	13
1.2 Study Rationale	13

11. Ethics and Responsibilities	33
11.1 Good Clinical Practice	33
11.2 Institutional Review Board	33
11.3 Informed Consent	34
12. Records Management	35
12.1 Source Documentation	35
12.2 Case Report Form Completion and Data Management	35
12.3 Study Files and Record Retention	36
13. Auditing and Monitoring	36
13.1 Protocol Adherence and Deviations	37
14. Amendments	37
15. Study Start and Termination	38
16. Confidentiality	38
17. References	38

Schedule of Events

Visit Weeks/Days	Screening Period	Treatment Period	
	Screening / Baseline Day -6 to Day 1	Week 1 Day 3 (+2)	Week 2 (EOS/ET) Day 14 (+6)
Informed Consent	X		
Eligibility Confirmation (Inclusion/Exclusion)	X		
Demographics	X		
Psychiatric History	X		
Prior & Concomitant Medications/Therapy	X		X
[REDACTED]	[REDACTED]		
[REDACTED]	[REDACTED]		[REDACTED]
[REDACTED]	[REDACTED]		[REDACTED]
Participant Identity Verification ^a	X		
Randomization	X		
Register within the Study Application	X		
CSQ-8 ^b			X
[REDACTED]		[REDACTED]	[REDACTED]
[REDACTED]		[REDACTED]	[REDACTED]
[REDACTED]		[REDACTED]	[REDACTED]
[REDACTED]			[REDACTED]
Assessment of AE/SAEs			X
App Engagement Metrics (collected throughout study)			X
Termination of App Access			X

^a Video call with designated study team member ^b Self-Report Clinical Assessment
EOS = End of Study
CSQ-8 = Client Satisfaction Questionnaire; [REDACTED]

Participants will have up to one week from the time of providing informed consent to complete all screening and baseline tasks including registering for the study application. Participants will not be withdrawn for failing to register for the app. Date of randomization will be considered Day 1.

1. Introduction

1.1 Background

Conversational agents (also known as chatbots) create an interactive experience through a sustained dialogue with a user. To date, the vast majority of these agents use rule-based logic that enables pre-written responses to be served up in response to user inputs (either free-text or button presses). The nature of these interactions can limit how personalized any conversation can be as responses are not based on understanding of the full nature of the content a user is expressing. Large Language Models (LLMs) provide the opportunity to better understand natural language and generate responses based on this understanding. As such, LLMs may enable more naturalistic conversations with personalized responses based on a fuller understanding of the intent expressed in a user's statement.

1.2 Study Rationale

The overarching goal of this study is to explore the feasibility and acceptability of a Minimally Viable Product (MVP) of Woebot, a natural language powered relational agent, that leverages LLMs to augment core therapeutic experiences. In a previous study, results demonstrated that Woebot is able to establish levels of therapeutic bond equivalent to those of a human mental health professional¹. Here, this study is looking to explore how integrating LLMs into Woebot impacts both the user experience of Woebot as well as the therapeutic bond that drives the relational agent mechanism of behavior change.

1.3 Investigational Device

Woebot is an automated relational agent based on researched and scientifically validated psychotherapies, primarily CBT, and accessible via iOS and Android applications.

The Woebot LLM MVP (referred to as MVP moving forward) is a minimal version of Woebot [REDACTED]

[REDACTED] the MVP will be compared against a version of Woebot that contains the same scope of features, but does not use LLMs. For safety, both the MVP and control will use the established Language Detection Protocol (see section 8.5.2 for more details).

2. Objectives

2.1 Primary Aim

- To explore user satisfaction with the DISC-MVP
 - Endpoint:
 - Client Satisfaction Questionnaire (CSQ-8) for both treatment groups

2.2 Secondary Aim

- To explore user satisfaction with the DISC-MVP for users with mild symptomatology or above (i.e., baseline PHQ-8 or GAD-7 ≥ 5)
 - Endpoint: CSQ-8 for both treatment groups.

3. Study Design

[figure not shown]
3.1 Description of Trial Design

This study is a double-blind, randomized controlled trial (RCT) exploring user satisfaction with an augmented version of Woebot and a previous version of Woebot among a sample of adults. Participants who consent and meet study eligibility criteria will be randomized 1:1 into one of the 2 arms. Study participation is up to 4 weeks in total, including a 1 week screening/baseline phase followed by a 2 week active intervention phase, and 1 week to complete the final study survey.

Participants will be recruited and enrolled into the study by Lindus Health . All remaining data collection and study monitoring will be managed through the Citrus decentralized trial platform managed by Lindus Health and by designated Woebot Health study personnel.

Self-report survey assessments will be administered to all participants at Screening/Baseline, Day 3, and Week 2. Members of the study team may contact participants through the Citrus platform via phone/sms and/or email to remind participants to complete study activities.

3.1.2 Participant Journey Flowchart

3.3 Participant Assignment, Randomization, and Blinding

3.3.1 Participant Assignment

Following confirmation of eligibility, participants will be randomly assigned to one of the two treatment groups.

3.3.2 Randomization

Randomization into the treatment arms will be 1:1 with no additional stratification by group demographics. The study may over enroll in order to meet 75 completed participants in each treatment arm. Participants will be considered randomized once they complete all of their screening and baseline activities including surveys, their identity has been verified, and eligibility has been confirmed (e.g., checked for duplicate registrations).

[figure not shown]
[figure not shown]

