10.2.4 Analysis Plan

[figure not shown]
Statistical analysis will be descriptive. Analyses will be restricted to users in each group that had a score of 5 or above on the PHQ-8 and/or the GAD-7 at baseline. The total scale score from the CSQ-8 will be summarized continuously for both treatment groups as well as overall.

[REDACTED]

[REDACTED]

[REDACTED]

[REDACTED]

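### Optional low-cost improvement: stratify randomisation by the baseline PHQ-8/GAD-7 threshold (≥5) that defines the secondary analysis population

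*Combined protocol and SAP*

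**What the plan says.** On allocation, section 3.3.2 states "Randomization into the treatment arms will be 1:1 with no additional stratification by group demographics". No stratification factor and no block scheme is named anywhere in the readable text. The same section fixes the order of events: "Participants will be considered randomized once they complete all of their screening and baseline activities including surveys".

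The synopsis gives the target population as "Adults with or without clinical symptoms", and sections 5.1.1 and 5.1.2 set no symptom threshold for entry. The secondary aim in section 2.2 is "To explore user satisfaction with the DISC-MVP for users with mild symptomatology or above". Section 10.2.4 carries this out with analyses "restricted to users in each group that had a score of 5 or above on the PHQ-8 and/or the GAD-7 at baseline". Section 10.2.2 expects the two arms to be descriptively similar within that group, so the question is a between-arm one.

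The only size target is for whole arms: "The study may over enroll in order to meet 75 completed participants in each treatment arm". Sections 10.1.4 and 10.2.4 summarise the CSQ-8 total by arm and overall, with no adjustment for baseline symptoms.

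**The concern.** The factor that defines the secondary population is mixed in the enrolled sample and should be known when each participant is allocated, yet the readable plan does not use it in the allocation. Two quantities are then uncontrolled: the number of symptomatic participants in each arm, which sets the precision of the secondary summary, and the symptomatic share in each arm, which could move the primary CSQ-8 comparison if satisfaction depends on symptom status.

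Both hypotheses will be judged by setting arm summaries side by side, without a test, margin or adjusted estimate. Baseline comparability therefore carries more of the interpretation than it would in an adjusted analysis.

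**Working it through.** **The plan's own figure.** Section 5 randomises about 165 to obtain 150 completers at 10% attrition. 150 × 1.10 = 165, and 150 / 0.90 = 166.7, or 167. The stated figure is reproduced closely enough for an approximate target. Section 9.3 reports no power calculation, so there is none to check.

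**Inputs.** From the documents: 150 completers, 75 per arm (3.3.2, section 5). Assumed, because the documents do not give it: the symptomatic share among completers, taken as 20% to 70%, or m = 30 to 105 people.

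**Model.** Without stratification, the number x of the m symptomatic completers who fall in one arm is hypergeometric (150 people, m symptomatic, 75 drawn). The difference in symptomatic share between arms is |2x − m| / 75. A 60:40 split or worse means that the smaller arm holds at most 0.4m. The standard error (SE) of the subgroup arm difference, relative to an even split, is √(1/x + 1/(m − x)) / √(4/m), averaged here over the distribution of x.

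| Assumed share (m) | P(60:40 or worse) | P(share differs by ≥10 points) | SD of difference in share | Mean rise in SE |
|---|---|---|---|---|
| 20% (30) | 31% | 15% | 6.6 points | 1.4% |
| 30% (45) | 15% | 15% | 7.5 points | 0.8% |
| 40% (60) | 7% | 24% | 8.0 points | 0.5% |
| 50% (75) | 2% | 19% | 8.2 points | 0.3% |
| 60% (90) | 0.4% | 24% | 8.0 points | 0.2% |
| 70% (105) | 0.03% | 15% | 7.5 points | 0.1% |

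The third column is not smooth because, for a fixed m, the count difference can take only even or only odd values.

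**What an uneven split costs.** At a 30% share the 95% range for one arm is 17 to 28 of 45. At 17 v 28 the SE ratio is √(1/17 + 1/28) / √(4/45) = 1.031, a rise of 3%. The smaller arm's own mean has an SE larger by √(22.5/17) = 1.15, or 15%. A 60:40 split gives √(1/0.6 + 1/0.4) / 2 = 1.021, a rise of 2%.

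**Effect on the primary comparison.** Shift = (CSQ-8 difference by symptom status) × (difference in symptomatic share). Taking an assumed 3-point difference, a 10-point imbalance gives 3 × 0.10 = 0.30 and a 15-point imbalance gives 3 × 0.15 = 0.45 CSQ-8 points. For scale, with an assumed CSQ-8 SD of 4 to 6, the SE of the arm difference is SD × √(2/75) = 0.65 to 0.98 points. Imbalances of 15 points or more occur in 2% to 7% of trials over the same range of shares.

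**With stratified blocks.** Taking blocks of 4 as an illustration, the arm difference within a stratum at randomisation is at most 2. Without stratification, the 95% bound on the subgroup count difference among completers is 10 to 12.

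**The case against.** The strongest reply is that this is an internal, exploratory and purely descriptive study (section 9.3), for which plain 1:1 randomisation is valid. The loss of precision is trivial on average, and a lopsided subgroup becomes rare once half or more of the sample is symptomatic. Section 10.5 already summarises baseline characteristics by arm, which would reveal an uneven mix if the scores are included. Restricting the secondary analysis to the symptomatic group also means that the proportion above the threshold cannot distort that comparison. All of this stands, and it limits the point to an optional improvement.

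Four stronger readings are tempting but unsupported:

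- A reader might infer that the primary comparison is biased. It is not: chance imbalance is random error, and the 0.3 to 0.45 point shift needs both an imbalance and an assumed 3-point effect.
- A reader might infer that the protocol regards symptom status as affecting satisfaction. Sections 2.2 and 10.2 only name a subgroup of interest, and 10.2.2 states the same expectation of similarity as 10.1.2.
- A reader might take section 3.3.2 as ruling out symptom stratification. Its words exclude only demographic factors. The absence of a symptom factor is inferred from the readable text, and a contents entry between 3.1.2 and 3.3 is redacted and some figures are not shown.
- A reader might expect stratification to remove the imbalance entirely, or to match the analysed set exactly. Section 9.2 analyses those with available survey data and a per-protocol subset, whereas stratification balances only those randomised.

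What survives is that the threshold is available before allocation, defines a stated analysis population, and could be balanced at almost no cost.

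**Conclusion.** The point holds as a cheap, optional design improvement. The readable plan leaves balance on the PHQ-8/GAD-7 threshold to chance, and a difference of 10 or more points in symptomatic share is fairly likely whatever the share within 20% to 70%. The risk of a 60:40 subgroup split depends strongly on that share and matters mainly if symptomatic participants are a minority. The consequence is modest in either case, and no stated conclusion of the study depends on it.

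These sizes rest on 75 completers per arm, the assumed range of shares and, for the primary shift only, the assumed 3-point difference in CSQ-8 by symptom status.

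**What to change.** In section 3.3.2, state that randomisation is 1:1 in permuted blocks of concealed, varying size, generated by the trial platform and stratified by baseline symptom status (PHQ-8 and/or GAD-7 ≥5 versus both <5). Concealed, varying block sizes matter because section 3.3.3 leaves some study staff unblinded.

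The cost is one protocol sentence and a two-stratum allocation list. The practical downside is that both scales must be scored automatically before allocation. No participants, visits or questionnaires are added. The change reduces imbalance among those randomised; attrition can restore some of it among completers and in the per-protocol set.

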3.3.3 Blinding and Unblinding

Participants will be blinded to their assigned treatment group. The primary research associate and project manager remain unblinded. Every effort will be made to keep a majority of the research staff blinded including study PI (unless there is a safety event which would require them to become unblinded for follow-up) and those conducting study analyses.

4. Trial Intervention

4.1 Study Conditions

Both treatment conditions will be available through a bespoke study app called the ‘Build’ app and will be made available exclusively for study participants through unique access codes.

4.3 Trial Intervention Compliance

Trial intervention compliance will not be monitored in this study and participants will not be removed from the study for failing to register and/or not regularly engaging with their assigned treatment. Instead, intervention compliance will be assessed post study during analysis. Compliance may be defined as opening the app at least once per week for a minimum of 50% of weeks (1 of 2) during the intervention period.

5. Study Population

Participants will be recruited through the Lindus Health CitrusRecruit network which utilizes a combination of participant sources including but not limited to existing patient databases, primary care networks, and targeted social media campaigns. Those interested in participating will be invited to complete a survey to confirm they meet the pre-screening criteria (excluding questions about suicidal ideation and attempt) and be presented with the opportunity to independently review and electronically sign the study consent form. Upon signing the consent form, participants will be asked to schedule a video call during which a designated member of the virtual site team will verify the participants identity. After successful completion of the verification call, participants will be provided with a secure link to complete the screening/baseline survey. Participants will be asked questions about their current suicidal ideation with plan and/or intent as well as an attempt in the past 12 months. People who do not meet study criteria based on suicidal ideation/attempt will be notified that they may benefit from a level of care beyond the scope of the study and that if they feel they are in need of immediate medical care they should contact 911 or go to their nearest emergency room and reach out to someone they trust that can help them stay safe. Additional resources will also be provided electronically. If a participant endorses

presence of current suicidal plan and/or intent, the study PI will attempt to follow-up with the participant (up to three times). See Section 8.5.1 of this protocol for more details.

Approximately ~165 adults will be randomized for this study to ensure a final sample of 150 completers (e.g., randomized and completed all study activities through Week 2; assuming a 10% attrition rate).

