5.3 Withdrawal of Participants from the Study

If a participant decides to withdraw consent from the study, they will be removed from future study activities and any data collected before withdrawal may be retained and used in study analyses. In addition, a participant may be withdrawn by the investigator if the participant violates the study plan, or for administrative and/or other safety reasons.

Discontinuation of study treatment for a participant occurs when study treatment is stopped earlier than the protocol planned duration and can be initiated by either the participant or the investigator. The investigator must discontinue study treatment for a given participant if he/she believes that continuation would negatively impact the participant's well-being. Involvement in the study is strictly voluntary. Participants have the right to withdraw from the study at any time for any reason, without any reprisal.

Participants should be discontinued from the study if any of the following occur:

1. It is discovered that the participant shared app images/screenshots publicly
2. The participant withdraws consent to participate in the study
3. The participant develops an illness that would interfere with their continued participation in the study
4. The participant has an SAE rated as Grade 3 (severe) or higher (see Section 8.3.2)
5. The participant is noncompliant with treatment schedule, study procedures, in the opinion of the investigator and per the protocol, where applicable
6. The PI, Sponsor, IRB, or regulatory agency requests withdrawal of the participant
7. Any other reason relating to the participant's safety or integrity of the study data as determined by the Safety Assessment Committee (SAC)

Participants who withdraw or are withdrawn from the study may be replaced. Participants who withdraw or are withdrawn from the study cannot subsequently rejoin the study.

If a participant withdraws or is withdrawn from the study for reasons related to safety, the study Sponsor-Investigator and SAC will be informed immediately.

If the participant withdraws consent for disclosure of further information, the Sponsor-Investigator may retain and continue to use any collected data before such a withdrawal of consent.

Although a participant is not obliged to give a reason for withdrawing from a study, the investigator should make a reasonable effort to ascertain the reason, while fully respecting the participant's rights.

6. Study Assessments and Procedures

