9.3 Sample Size Determination

Given that this study is for internal exploratory purposes and is relying on descriptive statistics for analyses, no power analyses were conducted. The N of 165 with a 10% attrition rate was determined based on the necessary N for meaningful internal learning.

10. Statistical Methods

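### Does randomizing about 165 at 10% attrition fall short of the 150 completers the plan says it secures?

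*Combined protocol and SAP*

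**What the plan says.** Section 5 (Study Population) holds the full statement: "Approximately ~165 adults will be randomized for this study to ensure a final sample of 150 completers", with the qualifier "assuming a 10% attrition rate". Completers are described there as people who were randomized and finished every study activity through Week 2, so the 10% applies to those randomized.

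The other places each give part of it:

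- The synopsis, in its row for number of participants, has "165 (150 complete", preceded by a tilde and with no attrition rate.
- Section 9.3 has "The N of 165 with a 10% attrition rate was determined based on the necessary N for meaningful internal learning", with no completer target. It also says that "no power analyses were conducted".
- Section 3.3.2 sets the allocation ("Randomization into the treatment arms will be 1:1") and adds: "The study may over enroll in order to meet 75 completed participants in each treatment arm".
- Section 5.3 adds: "Participants who withdraw or are withdrawn from the study may be replaced".

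**The concern.** A loss of 10% among those randomized means dividing the completer target by 0.90. The figure of 165 is what results from multiplying the target by 1.10, a common slip that always gives too small a number. The sentence also claims that 165 will ensure 150 completers, although at the plan's own attrition rate the expected number is below 150.

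If the completer count supported a power calculation or a decision rule, an understated randomized number would leave the trial short of its stated operating characteristics. Because section 9.3 reports no power analysis, the size and attrition figures are also the only numerical basis given for the sample size, so a mismatch between them is easily noticed.

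**Working it through.** **Inputs.** About 165 randomized (synopsis, sections 5 and 9.3); 150 completers (synopsis, section 5); 75 per arm (section 3.3.2); attrition 10% (sections 5 and 9.3); allocation 1:1 (section 3.3.2).

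**Reproducing the plan's figure.** 150 × (1 + 0.10) = 165, an exact match and the likely origin.

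**The division form.** 150 / (1 − 0.10) = 166.7, so 167 in total, with 167 × 0.90 = 150.3 completers expected. Rounding up within arms, 75 / 0.90 = 83.3, so 84 per arm or 168 in total, with 168 × 0.90 = 151.2 expected.

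**Forward from 165.** 165 × 0.90 = 148.5 completers, or 74.25 per arm. The shortfall is 150 − 148.5 = 1.5 completers (1.5 / 150 = 1.0%). In randomized participants it is 167 − 165 = 2 (2 / 167 = 1.2%). The attrition that takes 165 to 150 is 15 / 165 = 9.1%.

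**Chance of reaching the target without over-enrolment.** Assume independent dropout at a true rate of exactly 10%; the documents give no distribution. For both arms reaching 75, the split is taken as equal or nearly so.

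| Randomized | Expected completers | P(at least 150 complete) | P(both arms reach 75) |
|---|---|---|---|
| 165 (82/83) | 148.5 | 0.41 | 0.23 |
| 167 (83/84) | 150.3 | 0.59 | 0.37 |
| 168 (84/84) | 151.2 | 0.68 | 0.45 |

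Even 84 per arm misses the per-arm target more often than it meets it; on the same assumptions 85 per arm (170) is the first equal split to pass one half, at 0.60. The low per-arm probability therefore comes mainly from chance variation around the expected number, and the multiply-or-divide slip adds only part of it. What deals with chance variation is the freedom to keep enrolling, which the plan has.

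**Effect on the primary summary.** The 95% half-width for a difference in mean CSQ-8 is 1.96 × SD × √(2/n), with n per arm. The documents give no SD. Assuming 5 points:

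- n = 75: 1.96 × 5 × √(2/75) = 1.60
- n = 74: 1.96 × 5 × √(2/74) = 1.61

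The ratio of the two is √(75/74) = 1.007 whatever the SD, so the conclusion does not depend on the assumed value.

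**What uses the 150.** Section 9.2 defines the intent-to-treat sample as those randomized who have survey data, and the per-protocol sample by conduct. Neither has a minimum size. Sections 10.1.4 and 10.2.4 plan descriptive summaries only. The completer count enters no formula, test or threshold.

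**The case for a change.** The best case for an edit is that the plan does not say about 150 are expected; it says 165 will ensure 150. At its own rate 165 reaches 150 in only about 41% of cases, so over-enrolment becomes the likely route to the target, while the synopsis and section 5 read as though 165 were enough. Over-enrolment and replacement are both worded as permissions, without a trigger or a cap, and neither makes 165, 10% and 150 agree.

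Part of this stands. The arithmetic is correct, and ensure is too strong for any fixed number under random attrition. But all three figures meet only in the section 5 sentence, where 165 is marked as approximate twice over, and a discrepancy of about 1% is within what that marking covers. Both permissions serve the completer target, and a shortfall of one or two people is what they are there to absorb. That 165 is odd is no fault either: 82 and 83 is an ordinary outcome of 1:1 allocation with an approximate total.

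**Conclusion.** No change to the plan is needed. The planned number is about two participants lower than exact division by the retention rate would give, equivalent to 1.5 completers or about 1%. Followed as written, the plan can still reach 75 completers per arm through over-enrolment and replacement. If it ended at 74 per arm, interval width would change by under 1% and no conclusion would move.

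The probabilities above rest on independent dropout at exactly 10%, a rate for which the plan gives no source. The conclusion does not rest on them. It rests on the approximate marking, the provisions in sections 3.3.2 and 5.3, and the absence of any analysis that depends on exactly 150. It would be different if a power claim or a success criterion were tied to the completer count, and none is stated.
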